**Table 4-1 Protocol deviation codes and analysis sets**

Category Deviation code	Text description of deviation	Data exclusion
Subjects are excluded from all (safety) analysis in case of these PDs:		
12	Written ICF not obtained	Exclude subject completely from all (safety) analysis sets
Subjects are excluded from PK analysis in case of these PDs:		Exclude subject from PK analysis set

*TRTD01      Study drug dosing error or incorrect treatment administered.*

---

Subjects are excluded from PD analysis in case of these PDs:		Exclude subject from PD analysis set
COMD01	Used prohibited treatment within 24 hours before receipt of study drug and within the first 30 minutes post dose.	
TRTD01	Study drug dosing error or incorrect treatment administered. Predose severity of CH is not at least moderate at one of the periods (unless there was a diary entry error)	Corporate Confidential Information

If updates to this table are needed, an amendment to the SAP needs to be implemented prior to DBL

## **5       Statistical methods for Pharmacokinetic (PK) parameters**

Corporate Confidential Information

### **5.2      Descriptive analyses**

SOM230 plasma concentration data will be listed by treatment, subject, and visit/sampling time point. Descriptive summary statistics will be provided by treatment and visit/sampling time point, including the frequency (n, %) of concentrations below the LLOQ and reported as zero.

Summary statistics will include mean (arithmetic and geometric), SD, CV (arithmetic and geometric), median, minimum and maximum. An exception to this is Tmax where median, minimum and maximum will be presented. Concentrations below LLOQ will be treated as zero in summary statistics. A geometric mean will not be reported if the dataset includes zero values. The PK parameters will be listed by treatment and subject.

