management. If applicable and feasible, subjects in Period 1 may return to the study center for follow-up within 24 hour post treatment administration. The subjects will have a follow-up visit within 24 hours of the study drug administration in Period 2 where a pharmacokinetic (PK) sample will be collected, with a second PK sample collected 1 to 2 hours after the 1st PK sample. In case the follow-up visit in Period 2 falls on a weekend, a window of up to 48 hours may be considered.

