case of concomitant use of sumatriptan, and the relatively longer study period, patients will be allowed to only use 100% oxygen as rescue-medication, and a conventional randomized cross-over design seemed unsuitable. The use of placebo will allow unbiased assessment of the benefit of SOM230 using subjective endpoints. Consecutive assessment of the 1.5mg dose followed by assessment of low dose (0.9 mg s.c.) will provide cluster headache patients with a better chance of getting efficacious doses with a potential for earlier relief of pain and possibly a longer interval till the next attack. Inclusion of the two SOM230 dose levels in cohort 1 and cohort 2 will provide the opportunity to determine the dose response relationship and obtain initial estimates of the treatment differences in efficacy parameters.

Due to the medical condition, it is not possible to collect PK samples during an attack. Samples will therefore be collected during the visit following an attack after drug administration in each period.

Corporate Confidential Information

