## **6.7 Treatment exposure and compliance**

Pharmacokinetic parameters (measures of treatment exposure) will be determined in all subjects treated with [SOM230], as detailed in [Section 8.5](#).

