## 8 Procedures and assessments

**Table 8-1 Assessment Schedule, (Cohorts 1 &2)**

 Visit structure given for internal programming purpose only.

 In the event the subject requires SOC treatment for CH or a recurrent CH attack, the subject must contact the site, every effort must be made to discontinue the subject after 24 hours of taking the study medication, all EOS evaluations should be performed if a subject is discontinued.

 If subject is not domiciled in a clinic for the study, study drug will be administered at home, before study visits.

 If possible in Period 1, the subject may have a follow-up visit as soon as possible within 24 hours of the dose. The collected PK sample must be obtained as soon as the patient arrives to the clinic. The date, time and the time the subject took the study medication must be collected on the eCRF. If logistically not possible the sample may be collected by a visiting nurse or equivalent.

4-a In Period 2, the subject must have a follow up visit as soon as possible within 24 hours of the dose for ECG & to collect PK samples. The sample must be collected as soon as the patient arrives to the clinic. If logistically not possible the sample may be collected by a visiting nurse or equivalent. The date, time and the time the subject took the study medication must be collected on the eCRF. In case the follow-up visit in Period 2 falls on a weekend, a window of up to 48 hours may be considered.

 A second PK sample will be collected 1-2 hours after the 1st sample was collected; the collection time of PK samples must be entered in eCRF. The second PK can be optional if not logistically possible.

 If subject is not domiciled in a clinic for the study, the study drug and instructions for use will be dispensed to the subject to be used as out-patient.

 Subjects will take 2 injections (in Cohort 1) / 1 injection (in cohort 2) of SOM230 or placebo s.c. in each study Period (1 &2) as instructed. These injections must be administered at the same time one after the other. The date and time of dose must be recorded on the patient diary.

 Diary: issued at screening visit; baseline information should be collected only for last 3 days prior to the baseline visit. Diary will be reviewed at the clinic visits.

 Blood chemistry should be repeated if Baseline Visit is greater than 10 days from Screening Visit.

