## **6.2.2 Pharmacokinetic/pharmacodynamic interactions**

The relationship between reconstructed individual PK profiles with various efficacy/PD variables will be explored as appropriate and the results reported in a separate report.

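### SAP 5.2 summarises Tmax, but one sample on arrival at the follow-up visit and an optional second 1–2 hours later cannot measure it

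*SAP*

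**What the plan says.** SAP 5.2 lists summary statistics for the PK data and then adds: "An exception to this is Tmax where median, minimum and maximum will be presented". It continues: "The PK parameters will be listed by treatment and subject". SAP 5.2.1 plots mean and individual concentrations over time. SAP 6.2.2 carries the results further: "The relationship between reconstructed individual PK profiles with various efficacy/PD variables will be explored as appropriate", to be reported separately.

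The sampling is set out in the protocol. Section 3.1 places the follow-up visit "within 24 hours of the study drug administration in Period 2 where a pharmacokinetic (PK) sample will be collected", and allows more time at weekends: "In case the follow-up visit in Period 2 falls on a weekend, a window of up to 48 hours may be considered". A footnote to Table 8-1 adds: "A second PK sample will be collected 1-2 hours after the 1st sample was collected". The same footnote lets the second sample be omitted for logistical reasons. Outpatients dose at home before the visit. Section 3.2 explains the late sampling: "Due to the medical condition, it is not possible to collect PK samples during an attack". Under Section 8.5, placebo samples are not assayed, so Period 1 contributes no SOM230 data.

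The method of deriving PK parameters (SAP 5 before 5.2, and parts of Protocol 8.5 and 11.5.3) is redacted. Only the footnotes of Table 8-1 could be read, not its grid.

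**The concern.** Tmax is the time of the concentration peak. Estimating it needs samples on both sides of the peak, or a model with enough data to inform absorption. Nothing in the readable sampling text provides either. Because the derivation is redacted, both routes have to be tested: Tmax taken from the samples as observed, and Tmax taken from a reconstructed profile.

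At stake is a line in the PK table that looks like a measurement. For an acute treatment judged at 30 minutes, readers would take Tmax as evidence on speed of absorption. A related risk arises in the exposure-response work. If an individual exposure value is mostly prior, a flat relationship with response may reflect lack of information rather than lack of effect.

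**Working it through.** The plan states no figure for this point, so there is none to reproduce.

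**Inputs from the documents.** Protocol 5.1 equates 3 days with 5 half-lives, so t½ = 72/5 = 14.4 h and k = ln 2/14.4 = 0.0481 per h. The gap between samples is 1–2 h. The first sample comes at up to 24 h (48 h at weekends). The primary endpoint is at 30 minutes.

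**Assumptions, not in the documents.** One compartment with first-order absorption at rate ka; residual CV 10–20% (15% in steps 2, 4 and 5); between-subject SD on the log scale 0.6 for ka and 0.3 for CL/F and V/F; visit times uniform over the windows shown.

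**Step 1: which sample is higher.** The true fall is 1 − exp(−0.0481) = 4.7% over 1 h and 1 − exp(−0.0963) = 9.2% over 2 h. The chance that the later sample reads higher is Φ(−k·gap/(√2·CV)). This is 37% (1 h) and 25% (2 h) at CV 10%, and 43% and 37% at CV 20%. Measurement error therefore plays a large part in which of the two times would be recorded as Tmax.

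**Step 2: observed Tmax.** Observed Tmax is the time of the higher sample. It was simulated for true Tmax of 0.25, 0.5, 1 and 2 h.

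| First sample | Median observed Tmax | Correlation with visit time |
|---|---|---|
| 1–4 h | 3.0–3.1 h | 0.72–0.76 |
| 2–24 h | 13.5 h | 0.99 |
| 24–48 h | 36.5–36.6 h | 0.99 |

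A hand check for the middle row: the median first sample is at (2 + 24)/2 = 13 h. The second sample wins in about 37% of subjects and adds 1.5 h on average, so 13 + 0.37 × 1.5 ≈ 13.6 h. True Tmax does not enter.

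**Step 3: what a late sample can see.** Per unit of dose/V, C(t) = ka/(ka − k) × (exp(−kt) − exp(−ka·t)), and Tmax = ln(ka/k)/(ka − k). True Tmax of 0.25, 0.5, 1 and 2 h corresponds to ka of 25.07, 10.89, 4.61 and 1.88 per h. Across these, the 12 h concentration runs only from 0.562 to 0.576 (ratio 1.025). The 30-minute concentration runs from 0.978 down to 0.601.

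**Step 4: model-based values.** The table gives the share of prior variance left after two samples 1.5 h apart, by importance sampling, for typical Tmax of 0.5 and 1 h. On the log scale AUCinf is a constant minus ln(CL/F), so it has the same share as CL/F.

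| First sample | Tmax | Concentration at 30 min | AUCinf |
|---|---|---|---|
| 1 h | 0.88–1.00 | 0.16–0.25 | 0.98 |
| 2 h | 0.98–0.99 | 0.19–0.38 | 0.96 |
| 6 h | 1.00 | 0.39–0.57 | 0.79 |
| 12 h | 0.99 | 0.77–0.87 | 0.42 |
| 24 h | 0.97–0.98 | 0.91–0.94 | 0.16 |
| 48 h | 0.97–0.98 | 0.78–0.84 | 0.25–0.26 |

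With a single sample at 24 h, the Tmax share is 0.97–0.99. Repeat runs move the 30-minute column by a few hundredths.

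**Step 5: slower absorption.** With ka of 1–4 per h, the Tmax share is still about 0.9–1.0 from a first sample at 4 h on. The exception is a first sample at 1–2 h with slow absorption. At ka = 1 per h, typical Tmax is ln(1/0.0481)/(1 − 0.0481) = 3.2 h, and the concentration rises from 0.615 at 1 h to 0.845 at 2.5 h (37%), which a model can detect. The share left is then 0.34 at 1 h and 0.61 at 2 h. Other metrics over ka 1–4 per h are better informed: about 0.15–0.23 is left for Cmax with a first sample at 1–4 h and 0.30–0.35 at 6 h, and 0.24–0.34 for AUC0–24 at 4–12 h.

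**The case against.** The strongest reply has four parts.

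First, the derivation is redacted, and SAP 6.2.2 already calls the profiles reconstructed. A population model may be specified, and handling of shrinkage may sit in the separate report. This stands: nothing here can be called missing. It does not rescue the Tmax line, because both routes fail.

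Second, no minimum sampling time is given. The Table 8-1 footnotes ask for an early visit, a nurse may take the sample elsewhere, and some subjects may be domiciled. So sampling many hours after dosing is an inference. This also stands. Early samples inform the 30-minute concentration reasonably well and, if absorption is slow, Tmax as well. An observed Tmax would still be one of the sampling times.

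Third, a reader might infer that individual exposure as a whole is unobserved and that the exposure-response work is empty. The documents do not support that. SAP 6.2.2 names no 30-minute metric, late samples inform AUCinf, and early ones inform Cmax. A reader might also extend the criticism to a two-sample half-life or an observed Cmax. Neither is visibly planned; they appear only in the list of definitions.

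Fourth, the study is non-confirmatory, and PK is not among the visible primary or secondary objectives. This stands and limits the weight of the point.

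**Conclusion.** The Tmax summary in SAP 5.2 reports something this sampling scheme does not measure. Read from the samples, it is the visit time under every window tried. Taken from a reconstruction, it is essentially the population prior, with about 90–100% of prior variance left for first samples at 4 h or later. The same holds at 1–2 h when typical Tmax is about 1 h or less. The exception is very early sampling combined with slow absorption.

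The concentration near 30 minutes is weakly informed mainly when the first sample comes at about 12 h or more. A flat exposure-response result is open to misreading only for metrics with high shrinkage.

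The half-life comes from the protocol. The compartment model, residual error, between-subject variability and visit-time distributions are assumptions. The observed-Tmax result hardly depends on them; the model-based shares do. This is a minor PK-reporting correction, and no efficacy conclusion changes.

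**What to change.** - **SAP 5.2:** delete the Tmax summary. If Tmax comes from the reconstruction, keep it only as a labelled model prediction, with its shrinkage beside it.
- **SAP 5.2 and 5.2.1:** summarise and plot measured concentrations against actual hours since dose, not only by visit. In step 3's model with Tmax 0.5 h, relative concentration is 0.912 at 2 h and 0.316 at 24 h, a 2.9-fold difference that pooling by visit would hide. The protocol already requires dose and sample times to be recorded.
- **SAP 6.2.2:** report shrinkage for each individual exposure metric used, and state that a flat relationship will not be read as absence of exposure-response where shrinkage is high. A numerical cut-off is a matter of choice; the documents give no basis for one.

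The cost is a wording change and slightly different PK outputs, with no new data or procedures. The one loss is that no trial-specific Tmax is reported.

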### **5.2.1 Graphical presentation of results**

Arithmetic mean (SD) and geometric mean (95% CI) plasma concentration data will be plotted across time.

Overlaying individual plasma concentration-time profiles will be generated along with concentration versus time profiles for individual subjects.

## **6 Statistical methods for Pharmacodynamic (PD) parameters**

### **6.1 Primary objective**

The primary objective of this study is to assess headache response of single s.c. dose of SOM230 compared to placebo in managing CH attack at 30 minutes post-dosing.

#### **6.1.1 Variables**

Percent (%) of subjects with headache response defined as very severe, severe, or moderate pain before dosing that becomes mild or nil at 30 minutes post-dosing is the primary variable.

#### **6.1.2 Descriptive analyses**

If the second cohort (0.9 mg dose) is assessed then cohort will serve as a grouping factor for all relevant data listings.

The headache response will be defined at each post-dose timepoint separately and will be summarized by cohort, treatment and visit/timepoint using frequency tables. Percentage of subjects having received 100% oxygen therapy or sumatriptan at each time point will be tabulated by cohort and treatment.

#### **6.1.3 Statistical model, assumptions and hypotheses**

A logistic regression analysis on the 30 minutes post-dosing data only with baseline headache severity (very severe, severe or moderate), CH type (episodic or chronic) and dose (0 for placebo, 1.5 mg or 0.9 mg for SOM230) as fixed effects will be used to assess the effect of SOM230 on headache response. Dose will be included as a categorical variable in the model. Placebo adjusted headache response rate will be provided. Headache response measurements after 100% oxygen therapy or sumatriptan will be set to missing, which will be considered as missing at random. The frequency and percentage of subjects with each response shall be displayed, along with the mean estimates, 90% confidence interval and p-value from the logistic regression analysis.

The following approaches will be taken if the 0.9 mg dose is assessed in the second cohort:

Placebo adjusted headache response rate will be obtained for each of the two SOM230 doses. A linear dose-response trend test will be constructed within the logistic regression framework using a contrast with the first order orthogonal polynomial coefficients. Pairwise comparisons and further dose-response assessments will be performed as appropriate. If there is no difference between the two SOM230 doses then a comparison between the pooled SOM230 treatment and placebo will be conducted.

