### 3.2 Rationale for study design

Based on the nature of the studied disease and PK characteristics of SOM230, a single s.c. dose will provide an assessment of effect of SOM230 in managing cluster headache attack as well as the time to next attack. It is expected that a single dose of SOM230 will relieve the cluster headache attack and will delay the time to next attack resulting in reduced number of attacks per day. Given the nature of the disease (repeated attacks up to 8 attacks/day for up to 2 months), the relatively long half-life of SOM230, and to ensure consistency between attacks, treating 2 consecutive attacks in a one-sequence two-period design with a placebo treatment in Period 1 will be appropriate to cluster headache patients and will increase the statistical power by taking advantage of a within-patient comparison in the absence of carryover effects. The treatment effect will be confounded with the period effect in this one-sequence 2 period study. However, this is not a major concern considering the 2 periods are  $\leq 3$  days apart and we are looking for a substantial treatment effect. Subjects will be blinded to the sequence of treatment to minimize any potential bias. The Investigator input in this study will not have any influence on study outcome being solely entered by the subjects in the e-diary, thus the Investigators don't need to be blinded. Considering the severe pain associated with CH, patients benefiting from sumatriptan are expected to continue their conventional management that successfully relieves their pain. Accordingly, enrolled population in the study is expected to be mainly composed of non-sumatriptan users. To avoid confounding AE evaluation in

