### **11.4.2 Statistical model, hypothesis, and method of analysis**

A logistic regression analysis with baseline headache severity, CH type, dose, and dose by time interaction as fixed effects and subject as a random effect will be used to assess the effect of SOM230 on headache response over time. Dose and time will be included as categorical variables in the model. Placebo adjusted headache response rate at each time point will be provided. Headache response measurements after 100% oxygen therapy will be set to missing, which will be considered as missing at random.

The following approaches will be taken if the 0.9 mg dose is assessed in the second cohort:

Placebo adjusted headache response rate at each time point will be obtained for each of the two SOM230 doses. A linear dose-response trend test will be constructed within the logistic regression framework using a contrast with the first order orthogonal polynomial coefficients. Pairwise comparisons and further dose-response assessments will be performed as appropriate. If there is no difference between the two SOM230 doses then a comparison between the pooled SOM230 treatment and placebo will be conducted.

A subgroup analysis for non-sumatriptan users may be conducted as needed.

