#### **6.1.3.1 Sensitivity analyses**

Subjects are able to take a rescue medication at least 30 minutes following study medication administration. As a sensitivity analysis, the logistic regression analysis shall be repeated on all timepoints, where only the timepoints with at least 50% of non-missing data will be kept.

The logistic regression analysis with baseline headache severity (very severe, severe or moderate), CH type (episodic or chronic), dose (0 for placebo, 1.5 mg or 0.9 mg for SOM230), time and dose by time interaction as fixed effects and subject as a random effect will be used to assess the effect of SOM230 on headache response. Dose and time will be included as categorical variables in the model. Placebo adjusted headache response rate at each time point will be provided. Headache response measurements after 100% oxygen therapy or sumatriptan will be set to missing, which will be considered as missing at random. The frequency and percentage of subjects with each response shall be displayed, along with the mean estimates, 90% confidence interval and p-value from the logistic regression analysis.

The sensitivity logistic regression will only be performed if the primary analysis indicates a significant result.

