#### **6.1.3.3 Graphical presentation of results**

If there are sufficient data to analyze, then the time to headache response, time to pain free response and time to recurrence curves, using Kaplan-Meier estimates will be constructed by dose. A clustered log-rank test for correlated survival data will be performed to compare the time to event curves between treatments while hazard ratios will be estimated by the Cox proportional hazard frailty model with CH type and baseline headache severity or frequency included as covariates as appropriate. If subjects do not have an event, they will be censored at their last available visit. These analyses will only be conducted if the primary analysis indicates a significant result and if there is sufficient data.

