#### **6.1.4 Supportive analyses**

The McNemar test with or without stratification by CH type may also be used to compare headache response rates between treatments at 30 minutes post-dosing only.

If there are sufficient data to analyze, a Cox proportional hazard model with dose and CH type as classification factors and headache severity as a time dependent covariate will be used to analyze time to 100% oxygen therapy or sumatriptan. A random subject effect will be included in the model as well to account for the correlation among measurements from the same subject. This model will only be performed if the primary analysis indicates a significant result and there is sufficient data.

Joint modelling of the headache response and time to 100% oxygen therapy or sumatriptan data may be attempted as appropriate. This analysis will only be performed if a good response rate at 30 minutes versus placebo is detected.

Finally to avoid reducing statistical efficiency due to analyzing the dichotomized data, the headache severity measurements over time may be analyzed using a proportional-odds model similar to the aforementioned logistic regression model.

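### The SAP's primary 30-minute model has no subject effect, so paired attacks are analysed as independent: the 90% CI is too wide, the test is conservative, and its p-value gates the models that do use the pairing.

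*SAP*

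**What the plan says.** - **SAP 4** limits the efficacy set to subjects dosed in both periods, so the 30-minute data hold two records per subject.
- **SAP 6.1.3** sets the primary analysis as "A logistic regression analysis on the 30 minutes post-dosing data only with baseline headache severity", CH type and dose, all fixed effects. It reports a placebo-adjusted response rate, a 90% confidence interval and a p-value.
- **Protocol 11.4.2** specifies a different primary model, over all time points: "dose by time interaction as fixed effects and subject as a random effect will be used to assess the effect of SOM230".
- **SAP 6.1.3.1** keeps the subject effect for the sensitivity model ("time and dose by time interaction as fixed effects and subject as a random effect will be used"), under a condition: "The sensitivity logistic regression will only be performed if the primary analysis indicates a significant result".
- **SAP 6.1.3.3** puts the clustered log-rank and Cox frailty analyses under the same condition: "These analyses will only be conducted if the primary analysis indicates a significant result and if there is sufficient data".
- **SAP 6.1.4** does so for the Cox model of time to rescue: "This model will only be performed if the primary analysis indicates a significant result and there is sufficient data". The McNemar test is not gated but is optional: it "may also be used to compare headache response rates between treatments at 30 minutes post-dosing only".
- **Protocol 3.2** defends the one-sequence design partly because it "will increase the statistical power by taking advantage of a within-patient comparison in the absence of carryover effects". Protocol 11.6 plans on a within-patient correlation of 0.25.

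**The concern.** The primary model treats 23 patients with two attacks each as 46 unrelated patients. With positive within-patient correlation, the variance of the treatment difference is overstated. The interval is then wider than its label says, the test rejects less often than its nominal level, and the precision used to justify the design is lost.

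The omission does not look like shorthand, because the next subsection of the SAP writes the subject effect out. The gates add to the cost. If a paired analysis would be positive but the unpaired test misses, the random-subject model and the time-to-event analyses are never produced, and the only paired 30-minute analysis left is one the SAP does not oblige anyone to run. SAP 6.2.1.3 carries the same approach to the pain-free endpoint. SAP 6.1.3.2 describes missing data in terms of a repeated-measures likelihood, which fits the sensitivity model but not the primary one.

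**Working it through.** **Inputs (Protocol 11.6).** n = 23 per cohort; placebo 30%; SOM230 72%; correlation 0.25; success requires an estimated difference of at least 30 points and at least 90% probability of an effect above zero; stated power about 80%. The 20- and 30-point effects below are my assumptions.

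**1. The plan's own figure.** Exact enumeration of all paired 2×2 tables gives 88.2% power for the success rule; a normal approximation gives 85.0%. At zero correlation the values are 84.8% and 81.5%. The simulation model is not described, so this does not show the stated 80% to be wrong, and nothing below depends on it.

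**2. Standard error of the difference.**
- Variances: 0.30 × 0.70 = 0.2100 and 0.72 × 0.28 = 0.2016.
- Covariance: 0.25 × √(0.2100 × 0.2016) = 0.0514.
- Pairing ignored: √(0.4116/23) = 0.134.
- Pairing used: √((0.4116 − 2 × 0.0514)/23) = √(0.3087/23) = 0.116.
- Ratio: 1.155, close to 1/√(1 − 0.25). The excess is about 5% at correlation 0.10 and 29% at 0.40.

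**3. Interval and test, large-sample.** The nominal 1.645 becomes 1.645 × 1.155 = 1.90 true standard errors. Coverage is therefore about 94.2%, and two-sided error is 5.8% instead of 10%.

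**4. Exact results, n = 23, no covariates, correlation 0.25.** Unpaired logistic Wald test against McNemar, one-sided 5%:

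| True rates | Logistic | McNemar | Logistic misses, McNemar significant |
|---|---|---|---|
| 30% vs 50% | 38.0% | 48.4% | 10.8% |
| 30% vs 60% | 69.5% | 77.9% | 8.8% |
| 30% vs 72% | 94.0% | 96.8% | 2.9% |

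With no effect (30% in both periods) the two-sided 10% rejection rates are 5.3% and 9.9%. The nominal 90% interval for the odds ratio covers 94–95%. At 30% vs 72% the mean half-width for the risk difference is 21.5 points unpaired and 19.8 points by paired t.

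**5. With severity and CH type in the model.** Simulation of 4,000 cohorts of 23; random-intercept data calibrated to marginal correlation 0.25; log odds ratios of −0.5 assumed for both covariates. Model-based against subject-clustered (Kauermann-Carroll) variance:
- coverage 93–94% vs 90–91%;
- one-sided size 3.3% vs 4.6%;
- power 40% vs 45% at 20 points, and 95% vs 96% at 42 points.

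A separate simulation with covariates unrelated to response also gave 93–94% coverage, with intervals 9–11% wider than clustered ones.

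**6. Protocol success rule.** Power is 88.2% with either standard error, because the 30-point estimate threshold is the binding condition.

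**The case against.** The strongest reply is that nothing decisive changes. The study is non-confirmatory and the error is conservative. The Protocol 11.6 rule is met equally often with the paired or the unpaired test at true effects of 0, 20, 30 and 42 points (0.8%, 25.0%, 55.9%, 88.2%). Every cohort lost at the gate has an observed difference below 30 points. This stands, and it limits the severity. It does not repair the interval and p-value that SAP 6.1.3 requires to be reported.

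Second, Protocol 11.6 defines statistical significance as at least 90% probability of a positive effect, which could be read as the gate level. The SAP does not say so. At one-sided 10% the miss rates fall to 10.0%, 6.1% and 1.4% at 20, 30 and 42 points. At two-sided 5% they are 8%, 8% and 4%.

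Third, not every later model is gated on this p-value. The proportional-odds model in SAP 6.1.4 carries no gate, and joint modelling has its own condition. Both are optional, and neither is a paired comparison confined to 30 minutes.

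Fourth, the no-covariate figures overstate the effect in the SAP's actual model, and the adjusted figures rest on assumed covariate effects. If Cohort 2 runs and the placebo data are pooled, the standard-error excess falls to about 9.5%. The comparison of the two doses is between patients and is not affected in this way.

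**Conclusion.** The concern holds and should be fixed. As written, the primary model ignores the pairing that the protocol's primary model and the design rationale rely on, and the SAP gives no reason. At correlation 0.25 the standard error is about 15% too large without covariates; the interval is about 10% too wide with them. The nominal 90% interval covers 93–95%. Power loss is 1–3 percentage points at the planned effect and 5–10 at an assumed 20-point effect.

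The direction depends on positive within-patient correlation, which the protocol assumes. Near 0.10 the loss is small; a negative correlation would reverse it (two-sided error 14.8% at −0.25 in simulation). The issue does not inflate false positives at the planned correlation and does not change the Protocol 11.6 success rule.

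**What to change.** 1. In SAP 6.1.3, fit the 30-minute model by GEE clustered on subject with the Kauermann-Carroll variance. Report the placebo-adjusted rate as a standardised risk difference with a 90% interval from that variance.
2. Name a fallback for when the covariate model separates: the mean within-patient difference with a paired-t 90% interval.
3. Make the 30-minute McNemar test a required supportive analysis.
4. Run the SAP 6.1.3.1 model whatever the primary result, and state the significance level for any gate that is kept.
5. Limit SAP 6.1.3.2 to models with a subject term, and apply the same changes to the pain-free endpoint.

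**Cost.** SAP wording and a few lines of code; no new data. The correction must be named in advance. At n = 23, uncorrected clustered or paired-Wald intervals cover 87–90%, while Mancl-DeRouen with a t reference covers 93–94% and gives the gain back. Adding a random intercept to the 30-minute model is not the best repair: its likelihood-ratio test rejected 13% at nominal 10%. The adjusted fit separated in 1–17% of simulated cohorts under assumed covariate effects, hence the fallback.
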